2.5 Exploratory Outcomes

The incidence of myocardial infarction (**MI**), stroke, systemic embolism, and cardiovascular (CV) mortality will be summarized by treatment group. In addition, information from the specific CRFs will be summarized for each treatment group.

2.6 Other Study Outcomes and Evaluations

Blood Urea Nitrogen (BUN) will be used for Urea Reduction Ratio (URR) analysis in the Safety population.

$$\text{URR} = (\text{Upre} - \text{Upost}) / \text{Upre} \times 100\%$$

where U_{pre} is the pre-dialysis blood urea nitrogen (BUN) level in serum and U_{pos1} is the post-dialysis blood urea nitrogen (BUN) level in serum. The URR generated from Lab will be used.

URR and sp Kt/v values as well as the change and percent change from baseline will be summarized for each visit by treatment group for the safety population. Single pool dialyzer clearance of urea (sp Kt/v) from CRF will be used in the summary.

Change and percent change from baseline will be compared between each of the ISIS 416858-treated groups and the pooled placebo group using the ANOVA or Wilcoxon Rank Sum test, as appropriate. The normality will be tested by applying Kolmogorov-Smirnov test on the residuals (difference between individual values and group mean).

Changes in dialysis prescription will be listed.

2.6.J Platelet Function tests

All Flow cytometry and PFA results will be summarized by visit and treatment for Platelet Function/Activation Substudy population.

Flow cytometry results (and potentially a report with interpretation of the results) will be provided directly by Boston Children's hospital. Flow cytometry results of platelet-monocyte and platelet-neutrophil aggregates and platelet surface P-selectin and platelet surface activated GPIIb-IIa will be compared between each of the ISIS 416858-treated groups and the pooled placebo group.

The PFA results of duplicate closure times for each evaluated cartridges of collagen/EPI, collagen/ADP, and INNOVANCE PFA®P2Y (optional cartridge) for change and percent change from baseline will be compared between each of the ISIS 416858-treated groups and the pooled placebo group for subjects that have the PFA tests performed.

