1.4 Randomization & Treatment Allocation

Subjects will be randomized on Study Day 1 after all screening assessments have been completed and after the Investigator has verified that they are eligible. No subject may begin treatment prior to randomization and assignment of a unique subject identification number.

All subjects will be randomized using an automated system (IXRS). Subjects will be stratified based on the diagnosis of documented atrial fibrillation (AF) at Screening (Yes/No), enrolled in PK substudy (Yes/No), enrolled in Platelet substudy (Yes/No), and then subjects will be randomized to 1 of 3 dose cohorts in a 1:1:1 ratio (Cohort A, Cohort B, and Cohort C). Within each dose cohort, subjects will be randomized in a 3:1 ratio to receive treatment with Study Drug (either ISIS 416858 or placebo).

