2 ANALYTICAL PLAN

2.1 General Overview of Analyses

2.1.1 General Statistical Methods

Descriptive summary statistics including number of patients, mean, standard deviation, median, and range (minimum, maximum) for continuous variables, and counts and percentages for categorical variables will be used to summarize most data. All statistical tests will be conducted using 2-sided tests with 5% Type I error rate unless otherwise stated.

PK parameters will be summarized using number of patients, mean, standard deviation, coefficient of variation (CV), geometric mean, median, minimum, and maximum.

All analyses and tabulations will be performed using SAS® Version 9.2 or higher and Phoenix/WinNonlin version 6.1 or higher on a PC platform.

A separate analysis for on-treatment period might be provided if deemed necessary.

Pooled groups:

Patients who are placebo-treated will be pooled and analyzed as a single placebo group.

Patients who are ISIS 416858-treated may be pooled and summarized as the ISIS 416858 total group.

Baseline definition:

Unless otherwise specified, baseline for all safety laboratory results will be defined as the last non-missing measurement prior to the first dose. For post-dialysis Blood Urea Nitrogen (BUN) measures for Urea Reduction Ratio (URR) determination, post-dialysis baseline will be defined as the last non-missing post-dialysis measurement prior to the first dose

Analytical visits:

All post-baseline data will be summarized according to the visit windows in the table below. For patients who have multiple visits within a window, the average will be used in the summary for continuous variable and the worst case result will be used for categorical variable.

Table I Visit window for Clotting

Analysis visit	Visit window
Screening	<1
Baseline	last non-missing measurement prior to the first dose
Day8	[2, 11]
Day 15	[12, 21]
Day29	(22, 35]
Day43	[36, 49]
Day 57	[50, 63]
Day71	[64, 77]
Day 85	[78, 91]
Day99	(92, 105]

Day 113	[106, 116)
Day 120	[117, 126)
Day 134	(127, 140)
Day 148	(141, 154)
Day 162	[155, 168)
Day 176	[169, 182]
Day 190	(183, 196]
Day 204	[197, 210]
Day 218	[211, 224]
Day 232	[225, 238]
Day 246	(239, 252]
Day 260	[253, 266]

Table 2 Visit window for Vital Signs

Analysis visit	Visit window
Baseline	last non-missing measurement prior to the first dose
Day 5	(2, 6)
Day 8	[7, 9]
Day 12	[10, 13]
Day 15	[14, 17]
Day 22	[18, 25)
Day 29	[26, 32)
Day 36	[33, 39)
Day 43	[40, 46]
Day 50	[47, 53]
Day 57	[54, 60]

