3. EXPERIMENTAL PLAN

3.1 Study Design

This is a Phase 2 multicenter, double-blind, randomized, stratified, placebo-controlled study in ESRD subjects receiving hemodialysis at least 3 times per week for a minimum of 9 hours per week. Subjects will be stratified based on the diagnosis of documented atrial fibrillation (AF) at Screening (Yes/No), and then subjects will be randomized to 1 of 3 dose cohorts in a 1:1:1 ratio (Cohort A, Cohort B, and Cohort C). Additionally, subjects will be stratified by participation in the substudies. Within each dose cohort, subjects will be randomized in a 3:1 ratio to receive SC treatment with either ISIS 416858 or placebo (See [Study Design and Treatment Schema](#)). All standard of care hemodialysis therapies as prescribed by their providers, including heparins, will be continued.

Cohort A: 200 mg ISIS 416858 or placebo SC (3:1)
Cohort B: 250 mg ISIS 416858 or placebo SC (3:1)
Cohort C: 300 mg ISIS 416858 or placebo SC (3:1)

All cohorts will consist of up to 4-week screening period for procedures and a 26-week treatment period followed by a 12-week post-treatment evaluation period.

The SC Tolerability assessments using 0.9% sterile saline should be administered as 2 noncontiguous injections during the screening period on Study Days S-14 (\pm 3) and S-7 (\pm 3). Enrolled subjects will receive a SC dose of Study Drug (200 mg, 250 mg, or 300 mg ISIS 416858, or placebo) approximately weekly from Week 1 (Day 1) through Week 26.

The windows for study visits are specified in the Schedule of Procedures ([Appendix A](#)); please note that the Study Drug (ISIS 416858 or placebo) dose may not be administered more than once on the same day. Any questions on study procedures and visit windows may be directed to the Sponsor (or designee).

3.1.1 *Platelet Function/Activation Subgroup*

fu a subgroup of approximately 12 subjects in each cohort, platelet function and/or activation will be assessed. These subjects must have platelet counts that are $180,000/\text{mm}^3$ at Screening and who are not taking any anticoagulants or antiplatelet agents (other than aspirin).

At regularly scheduled visits during Weeks 1 (pre-dose), 12, 26, and 38, additional blood samples will be collected and processed for platelet function and/or activation tests as shown in [Appendix A](#).

3.1.2 *Pharmacokinetic Subgroup*

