10. STATISTICAL CONSIDERATIONS

10.1 Study Endpoints, Subsets, and Covariates

10.1.1 Safety and Tolerability

The primary safety outcome is the combination of MB and CRNMB during the treatment period (or early study termination). For the subgroup of subjects evaluated for platelet function and/or activation, an analysis of pre- and post-treatment results with ISIS 416858 may be conducted and compared to treatment with placebo.

The safety and tolerability of ISIS 416858 will be assessed by determining the incidence and severity of AEs and will be evaluated by reviewing:

- AEs (including bleeding events)
- Vital signs and weight
- Physical examination
- Clinical laboratory tests
- Coagulation parameters
- Use of concomitant medications

10.1.2 *Pharmacodynamic Outcomes*

- Change from Baseline in FXI antigen and activity
- Change from Baseline in aPTT
- The extent and frequency of clotting on the dialysis filters and circuit

10.1.3 *Exploratory Outcomes*

- Incidence of myocardial infarction (MI), stroke, systemic embolism, and cardiovascular (CV) mortality

10.1.4 *Other Study Outcomes and Evaluations*

- Urea Reduction Ratio
- PK

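### The platelet substudy comparisons (about 9 v 9 per dose) are planned without a confidence interval and leave baseline and repeat-visit information unused, so they are less precise than the scheduled samples allow

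*Combined protocol and SAP*

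**What the plan says.** Protocol 3.1.1 sets the size: in a "subgroup of approximately 12 subjects in each cohort, platelet function and/or activation will be assessed". Samples are taken pre-dose on Day 1, on Days 78 and 176 during treatment, and on Day 260 (protocol 6.1.3 and 6.1.4). SAP 1.4 makes substudy participation a stratification factor ("enrolled in Platelet substudy (Yes/No), and then subjects will be randomized to 1 of 3 dose cohorts in a 1:1:1 ratio") and randomizes 3:1 within each cohort. SAP 2.1.1 pools placebo across cohorts.

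SAP 2.6.1 summarizes flow cytometry and PFA results by visit and treatment. For flow cytometry, it then says that "platelet surface P-selectin and platelet surface activated GPIIb-IIa will be compared between each of the ISIS 416858-treated groups and the pooled placebo group". PFA closure times are compared between the same groups, as change and percent change from baseline, in subjects who had the test. SAP 2.6.1 names no test, model, visit or confidence interval for either. The general rule in SAP 2.1.1 (two-sided, 5%) therefore applies by default. For the active arms together, SAP 2.1.1 says only: "Patients who are ISIS 416858-treated may be pooled and summarized as the ISIS 416858 total group".

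Protocol 10.1.1 mentions the platelet work under Safety and Tolerability, in conditional terms: "an analysis of pre- and post-treatment results with ISIS 416858 may be conducted and compared to treatment with placebo". The SAP gives it a separate heading (1.3.5) and analyses it under Other Study Outcomes and Evaluations. Protocol 10.2 and SAP 2.1.3 state that the sample size has no statistical rationale.

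**The concern.** Protocol 2.5 names thrombocytopenia and increased bleeding as safety considerations. Platelet counts are followed in everyone, but the scheduled function and activation tests are confined to this substudy, so the results will be looked at. With about 9 subjects a side and one visit at a time, each estimate is imprecise. Without an interval the reader cannot see how imprecise it is.

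Part of that imprecision is unnecessary. Each subject already gives a pre-dose value and two on-treatment values. The plan does not say that flow cytometry uses the pre-dose value at all. For PFA it uses subtraction and percent change, which are generally less efficient than covariate adjustment. Neither analysis combines the two on-treatment visits.

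**Working it through.** The documents give no power, effect size or SD for the substudy, so there is no planned figure to reproduce. Effects are expressed in units of the between-subject SD. The 0.5-SD and 1-SD effects and the correlations are assumptions.

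**Group sizes.** Active per dose: 12 × 3/4 = 9. Pooled placebo: 3 cohorts × 12 × 1/4 = 9. Total active: 3 × 9 = 27. Stratifying on substudy participation supports the 3:1 ratio holding inside the substudy. Missing values are generally not imputed (SAP 2.1.5), so evaluable numbers can be lower.

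**Per-dose comparison, one visit, unadjusted (9 v 9, two-sided 5% t-test, 16 df).**
- Standard error = √(1/9 + 1/9) = 0.471 SD.
- 95% CI half-width = 2.120 × 0.471 = 1.00 SD.
- Noncentrality at 1 SD = 1/0.471 = 2.12, giving power 0.51 and a miss rate of 49%. At 0.5 SD, power is 0.17 and the miss rate 83%.
- Sensitivity at 1 SD: 0.54 with a four-group ANOVA error term (32 df), 0.45 with an exact Wilcoxon test (simulated), and 0.46 or 0.41 with 8 or 7 evaluable per group.

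**All three comparisons together.** If the tests were independent, the chance that all three miss a 1-SD effect common to all doses would be 0.49³ ≈ 0.12. They share one placebo group, so the chance is higher. By simulation, all three miss 24% of the time at 1 SD, 44% at 0.75 SD and 66% at 0.5 SD.

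**PFA on change from baseline.** With correlation r between visits, the SD of a change is √(2(1 − r)): 1.18, 1.00 and 0.77 for r = 0.3, 0.5 and 0.7. The single-visit half-width, 1.00 times these values, is 1.18, 1.00 and 0.77 SD. Subtraction helps only when r exceeds 0.5.

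**Two visits with Day 1 as covariate.** Assume a common correlation r among Days 1, 78 and 176, and the same effect at both on-treatment visits. The mean of the two on-treatment values has variance (1 + r)/2 and covariance r with baseline, so the residual SD = √((1 + r)/2 − r²). One further degree of freedom is spent on the covariate (15 df per dose, 33 df pooled).

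| r | Residual SD | 9 v 9: miss at 1 SD | 9 v 9: half-width | 27 v 9: half-width |
|---|---|---|---|---|
| 0.3 | 0.75 | 25% | 0.75 SD | 0.59 SD |
| 0.5 | 0.71 | 20% | 0.71 SD | 0.55 SD |
| 0.7 | 0.60 | 9% | 0.60 SD | 0.47 SD |

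For example, at r = 0.3 the per-dose half-width is 2.131 × 0.748 × 0.471 = 0.75 SD.

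**What pooling the doses does.** Unadjusted, 27 v 9 has power 0.71 at 1 SD (miss rate 29%) and half-width 0.78 SD when all doses share the effect. If a 1-SD effect occurs at one dose only, the pooled mean shift is 1/3 SD. Power is then about 0.13 unadjusted and 0.20 to 0.29 adjusted, against 0.51 for the planned test at that dose.

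**The case against.** The strongest reply is that this is an optional Phase 2 substudy, described as an analysis that may be done, in a trial that openly has no statistical basis for its size. No equivalence claim is made, so no margin is owed. That stands.

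It also disposes of several stronger readings that a reader might reach:

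- *A non-significant result will be taken as proof of no platelet effect.* No document says so or sets a success rule.
- *The substudy would miss a 1-SD effect half the time.* That is the rate for one comparison. When the effect is common to all doses, all three miss it about 24% of the time, although finding any one of three unadjusted tests significant carries no multiplicity control.
- *Platelet function is a listed safety outcome.* Protocol 10.1.1 mentions the analysis in a sentence outside its bulleted list, and the SAP files it under other outcomes. Platelet counts and bleeding are followed in all subjects.
- *The pooled active comparison should replace the per-dose ones.* Pooling alone still misses 29% at 1 SD and does poorly if only one dose has an effect. If the work is treated as safety, SAP 2.3 already presents safety summary tables with an ISIS 416858 total column, so a pooled descriptive summary is arguably planned.

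None of this answers the narrower point. SAP 2.6.1 commits to between-group comparisons but plans no interval and does not combine the information already scheduled.

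**Conclusion.** The point holds as avoidable imprecision and incomplete reporting, not as an error. As planned, each dose-versus-placebo comparison at a single visit, unadjusted, has about 51% power for a 1-SD effect. Even an observed difference of zero would leave effects of up to about 1 SD not excluded. Using the Day 1, 78 and 176 samples together narrows the per-dose interval by roughly 25% to 40%, from 1.00 to between 0.75 and 0.60 SD.

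This rests on about 9 evaluable subjects per group, approximately normal data, an assumed 1-SD effect present at both on-treatment visits, and an assumed common correlation of 0.3 to 0.7. The gain over the plan is smaller for PFA if its correlation is high, because change from baseline already captures part of it. Even the improved analysis does not exclude effects below about 0.6 SD per dose or about 0.5 SD pooled, so it remains exploratory.

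**What to change.** In SAP 2.6.1:

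1. Analyse each flow-cytometry and PFA measure with one repeated-measures model over Days 78 and 176, with treatment group, visit and the Day 1 value as covariate. Report each dose-versus-pooled-placebo difference, averaged over the two visits, with its 95% CI. Keep the by-visit summaries, including Day 260, as planned.
2. From the same model, add the ISIS 416858 total versus pooled placebo difference with its 95% CI as a supplement. Do not let it replace the per-dose comparisons, because pooling dilutes an effect confined to one dose.

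The cost is SAP wording and one extra model per measure. No new patients, visits or samples are needed.

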2.7 Pharmacokinetic Analysis

For pharmacokinetic (PK) assessment, plasma trough PK samples during the 26-week treatment period and post-treatment samples during the 12-week post-treatment follow up period will be collected from all patients in the study. Additionally, extensive plasma PK samples will be collected in the PK subgroup following the first (Day 1) and last (Day 176) SC administration.

PK analysis will be conducted for the PK Population only.

2.7.1 Plasma Concentration Data

Plasma concentrations of ISIS 416858 over time, along with the scheduled (nominal) and actual sampling times (i.e., time from SC dosing) will be listed (when applicable) for each

subject, by group/subgroup, cohort, treatment, and nominal dose. In addition, percent differences between scheduled and actual sampling times, and between nominal dose and actual dose received will also be listed for all patients.

For all patients who receive ISIS 416858 treatment, ISIS 416858 plasma trough and post-treatment concentrations will be summarized using descriptive statistics by cohort, nominal dose, study day, and scheduled time point, without and/or with stratification by subject IM status (see Section 3.8). ISIS 416858 plasma concentrations from the PK subgroup will also be similarly summarized. Plasma concentrations below the lower limit of quantification (LLOQ) will be presented as "BLQ". For the purpose of calculating typical descriptive statistics (n, mean, SD, %CV, geometric mean, geometric %CV, median, minimum, and maximum) for plasma concentrations, all BLQ values will be set to zero. Mean plasma concentrations that are BLQ will be presented as BLQ, and the SD and %CV will be reported as "NA" (not applicable). At the discretion of the PK scientist and/or biostatistician, samples may be excluded from descriptive statistics if there are large deviations between scheduled and actual sampling times, or large deviations between actual dose and nominal dose (e.g., percent difference between scheduled and actual sampling times, or between nominal and actual dose greater than 30%). Any samples excluded from the summary descriptive statistics, if deemed necessary, will be listed separately along with the reason for exclusion.

For all evaluable patients, ISIS 416858 plasma trough (predose) and post-treatment concentrations versus time (actual) profiles for each individual patient, as well as corresponding mean (\pm SD) plasma concentration versus time (scheduled) profiles will be presented graphically on linear and semilogarithmic scales, without and with stratification by subject immunogenicity status (see Section 3.8). For the PK subgroup, ISIS 416858 plasma concentration versus time (actual) profiles (up to 24 hours post dose and/or full profiles) following the dose on Days 1 and 176, as well as the mean(\pm SD) plasma concentrations versus time (scheduled) profiles without and/or with stratification by subject IM status, will be presented graphically on linear and semilogarithmic scales. At the discretion of the PK scientist and/or biostatistician, samples may be excluded from the mean plots if there are large deviations between scheduled and actual sampling times, or large deviations between actual dose and nominal dose (e.g., percent difference between scheduled and actual sampling times, or between nominal and actual dose greater than 30%).

2.7.2 *Plasma Pharmacokinetic Parameters*

Noncompartmental PK analysis of ISIS 416858 will be carried out on each individual patient data set where full PK sampling profiles and/or post-treatment profiles are collected using Phoenix WinNonLin Version 8.0 or higher (Pharsight Corp., Mountain View, CA). Plasma pharmacokinetic parameters in each subject (when applicable) will be determined. For calculation of PK parameters, all BLQ values will be set to zero. The following plasma PK

parameters will be calculated (when applicable and not necessarily limited to) and based on actual sampling times:

1. Cmax: the maximum observed ISIS 416858 concentration in plasma will be determined on Day 1 and Day 176 for patients in the PK subgroup only.
2. Tmax: the time at which Cmax occurs will be determined on Day 1 and Day 176 for the PK subgroup only.
3. AUC_{0-24hr}: partial area under the plasma concentration-time curve (AUC) from time zero to 24 hours will be calculated using the linear-up log-down trapezoidal rule on Day 1 and Day 176 for patients in the PK subgroup only.
4. AUC_{0-48hr}: partial area under the plasma concentration-time curve (AUC) from time zero to 48 hours will be calculated using the linear-up log-down trapezoidal rule on Day 176 for patients in the PK subgroup only.
5. AUC_{0-168hr} (AUC_t): partial area under the plasma concentration-time curve (AUC) from time zero to 168 hours will be calculated using the linear-up log-down trapezoidal rule on Day 176 for patients in the PK subgroup only.
6. CL_{ssIF} (L/hr): Plasma clearance at steady-state will be calculated from CL_{sJF} = Actual Dose/AUC_{0.168hr} for dosing on Study Day 176 for patients in the PK subgroup only.
7. V_{z/F} (L): Apparent volume of distribution in the terminal phase will be calculated from V_{z/F} = CL_{ssIF}/A_Z for dosing on Study Day 176 for patients in the PK subgroup only.
8. t_{1/2z}: apparent terminal elimination half-life will be calculated from the equation, t_{1mz} = 0.693/A_Z, where A_Z is the rate constant associated with the apparent terminal elimination phase. A minimum of three data points in the elimination phase will be used to define A_{vz} and the correlation of determination values (r²) has to be at or greater than 0.8 for the estimate to be accepted. This parameter will only be calculated following the dose on Day 176 for all evaluable patients (including subjects participating in the PK subgroup) receiving active study drug ISIS 416858 (i.e. **PK** set).

Plasma pharmacokinetic parameters (if applicable) will be summarized using descriptive statistics (n, mean, SD, %CV, geometric mean, geometric %CV, median, minimum, and maximum) by cohort, nominal dose, and day (as deemed appropriate).

Plasma pharmacokinetic parameters will be listed by cohort, dose, subject ID, subject IM status, and study day; and appropriately summarized (separately for the PK subgroup and all evaluable ISIS 416858 treated patients) using descriptive statistics (n, mean, SD, SE, %CV, geometric mean, geometric %CV, median, minimum, and maximum) by study day.

Additionally, subject IM status stratified (see Section 3.8) plasma pharmacokinetic parameters will be similarly summarized (again separately for the PK Subgroup and all

evaluable ISIS 416858 treated patients). Other stratifications may also be performed if deemed warranted at the discretion of the pharmacokineticist and/or biostatistician.

Exposure-response relationships between selected pharmacodynamic (including but not limited to FXI antigen level and FXI activity) and pharmacokinetic measures (including but not limited to plasma trough concentrations) may also be explored (including with and without stratification by IM status), where appropriate.

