2.1.5 Incomplete or Missing Data

In general, missing data values will not be imputed. Incomplete data handling rules will be described in the specified section if needed.

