
[figure not shown]
PROTOCOL SYNOPSIS *Continued*

Treatment Groups	
There will be 3-dose cohorts that will run concurrently. Subjects will be stratified based on the diagnosis of documented atrial fibrillation and then randomized to 1 of 3 dose cohorts in a 1:1:1 ratio (Cohort A, Cohort B, and Cohort C). Within each dose cohort, subjects will be randomized in a 3:1 ratio to receive subcutaneous treatment with either ISIS 416858 or placebo that is added to standard of care hemodialysis therapies as prescribed by their providers, including heparin.
 
Cohort A: Approximately 68 dialysis subjects will be randomized 3:1 to either 200 mg ISIS 416858 or placebo
 
Cohort B: Approximately 68 dialysis subjects will be randomized 3:1 to either 250 mg ISIS 416858 or placebo
 
Cohort C: Approximately 68 dialysis subjects will be randomized 3:1 to either 300 mg ISIS 416858 or placebo

Study Drug Dosage and Administration	
The SC Tolerability assessments using 0.9% sterile saline should be administered as two 0.75 ml noncontiguous injections on Study Days S-14 (\pm 3) and S-7 (\pm 3).
 
For Cohort A, B and C, the Sponsor will provide ISIS 416858 (200 mg/ml, 1.0 ml) and Placebo (1.0 ml). All doses are given by SC injection.
 
Study Drug will be administered SC post-dialysis at any time from when blood is being returned to the subject but must be within 2 hours (preferably within 15 minutes of dialysis conclusion) for a total of 26 consecutive weeks of treatment in all cohorts.
 
The injection volume will be 1.0 ml for Cohort A (200 mg), 1.25 ml for Cohort B (250 mg) and 1.5 ml for Cohort C (300 mg). Cohorts B and C will be administered Study Drug (ISIS 416858 or placebo) as 2 noncontiguous SC injections.

Rationale for Dose and Schedule Selection	Based on the PK/PD profile of ISIS 416858 in the previous Phase 1 (ISIS 416858-CS1) and Phase 2 (ISIS 416858-CS3 and ISIS 416858-CS4) studies, doses up to 300 mg of ISIS 416858 have demonstrated significant reduction in FXI activity and consequent anti-thrombotic effects without an increased bleeding risk.

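### Setting BLQ concentrations to zero makes the geometric mean 0 and the geometric %CV undefined in any summary cell where only some values are BLQ

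*Combined protocol and SAP*

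**What the plan says.** SAP 2.7.1 lists n, mean, SD, %CV and the geometric and order statistics for plasma concentrations, with one substitution for all of them: "geometric mean, geometric %CV, median, minimum, and maximum) for plasma concentrations, all BLQ values will be set to zero". The summaries are cut finely: "plasma trough and post-treatment concentrations will be summarized using descriptive statistics by cohort, nominal dose, study day, and scheduled time point", and may be split further by immunogenicity status.

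The only special handling of BLQ results in these statistics is: "Mean plasma concentrations that are BLQ will be presented as BLQ, and the SD and %CV will be reported as 'NA' (not applicable". It does not name the geometric statistics. Samples may be left out for timing or dose deviations ("samples may be excluded from descriptive statistics if there are large deviations between scheduled and actual sampling times"), but a BLQ result is not a listed reason.

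No other section supplies a log-scale rule. SAP 2.1.1 includes the geometric mean among the PK statistics without saying how zeros are treated. SAP 2.1.5 says only "In general, missing data values will not be imputed". Protocol 10.6.3.1 leaves further PK detail to the SAP. For derived parameters, SAP 2.7.2 has a parallel rule: "For calculation of PK parameters, all BLQ values will be set to zero".

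**The concern.** The plan names two log-scale statistics and prescribes an input for which the logarithm does not exist. This is a stated rule that gives a wrong result, not a missing detail. In a cell with a few BLQ values, the programmer must either print a geometric mean of 0 and no geometric %CV, or improvise. The likeliest improvisation is to drop the zeros. That removes the lowest values, biases the geometric mean upward, and puts a different n behind two statistics in the same table row.

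At stake is the readability and consistency of the geometric concentration summaries by dose, visit and antibody status, mainly where drug levels are falling towards the quantification limit.

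**Working it through.** The plan states no figure on this point, so there is nothing to reproduce. The check follows from definitions and illustrations.

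**Inputs from the documents**
- Active patients per dose: about 68 per cohort at 3:1 (Protocol Synopsis, Treatment Groups), so 68 × 0.75 = 51.
- PK subgroup: about 12 per cohort (Protocol 3.1.2), so 12 × 0.75 = 9 active if 3:1 holds within it.
- Half-life: the protocol equates 84 days with about 5 half-lives (Protocol 5.1), so 84/5 = 16.8 days.
- Post-treatment PK samples for all subjects: Days 190, 204, 232 and 260 (Protocol Appendix C). Last dose: Day 176.

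**Assumed, because the documents do not give them:** LLOQ, BLQ rates and the concentration distribution.

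**Step 1. Effect of one zero.** Geometric mean = exp(mean of ln x). Geometric %CV = 100 × √(exp(SD(ln x)²) − 1). With any x = 0, the geometric mean is 0 and SD(ln x) does not exist. On simulated lognormal values (median 20, log-SD 0.6, arbitrary units), with the lowest value set to zero:

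| | n = 51 | n = 9 |
|---|---|---|
| Arithmetic mean | 22.45 → 22.38 | 20.3 → 19.3 |
| Median | 20.4, unchanged | 16.6, unchanged |
| Geometric mean | 19.7 → 0 | 18.2 → 0 |
| Geometric %CV | 57% → undefined | 54% → undefined |

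The arithmetic mean stays far above any plausible LLOQ, so the fallback for a mean that is BLQ is not triggered.

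**Step 2. Chance that a cell holds a BLQ value.** P = 1 − (1 − p)^n, assuming independent samples and no dropout.
- n = 51: 40% at p = 1%, 64% at 2%, 93% at 5%, 99.5% at 10%.
- n = 9: 9%, 17%, 37% and 61%.

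**Step 3. Where BLQ values are plausible.** Fraction remaining = 0.5^((day − 176)/16.8), assuming a single-exponential decline: Day 190, 56%; Day 204, 31%; Day 232, 10%; Day 260, 3%.

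**Step 4. Size under two repairs.** Assume a lognormal with geometric mean 20 and CV 80%, so σ² = ln(1 + 0.8²) = 0.495 and σ = 0.703. For a BLQ proportion p, let z = Φ⁻¹(p) and λ = φ(z)/(1 − p).
- Implied LLOQ = 20 × exp(σz).
- Geometric mean with zeros dropped = 20 × exp(σλ); log-variance = σ²(1 + zλ − λ²).
- Geometric mean with LLOQ/2 = exp[p ln(LLOQ/2) + (1 − p)(ln 20 + σλ)].

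| p | λ | LLOQ (as % of 20) | Zeros dropped: GM (bias), geometric CV | LLOQ/2: GM (bias) |
|---|---|---|---|---|
| 2% | 0.049 | 4.7 (24%) | 20.7 (+3.5%), 75% | 19.8 (−1%) |
| 10% | 0.195 | 8.1 (41%) | 22.9 (+15%), 65% | 19.3 (−4%) |
| 20% | 0.350 | 11.1 (55%) | 25.6 (+28%), 58% | 18.8 (−6%) |

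The larger biases arise only where the LLOQ is about 41% to 55% of the geometric mean.

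**The case against.** The strongest reply is that the SAP anticipates BLQ values and says how to show them. Where nearly everything is BLQ, such as the Day 1 pre-dose sample, the mean is BLQ, is printed as such, and little is lost. A geometric mean of 0 is also below the LLOQ, so the same sentence could be stretched to print it as BLQ. The first part stands. The second does not help: one BLQ sample among 51 would then print BLQ beside an arithmetic mean of about 22.

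It is also fair that the arithmetic mean, median, minimum and maximum remain usable under the zero rule, and that the planned mean concentration plots in SAP 2.7.1 use the arithmetic mean and SD. A reader might infer that the main PK displays fail. Nothing in the documents ranks the geometric mean above the other statistics. PK is named in the primary objective, but SAP 1.3.4 lists it among other outcomes, and no test rests on these summaries.

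A reader might also infer that the AUCs and other parameters in SAP 2.7.2 are invalid. The documents do not show this. A zeroed concentration does not normally make a parameter zero. The AUCs are partial areas in the PK subgroup, up to 24 hours on Day 1 and up to 168 hours on Day 176. Protocol 2.3.3.2 reports mean Cmax 12.0 µg/mL and AUC over 24 hours of 150 µg·hr/mL after a single 300 mg dose. That averages 150/24 = 6.25 µg/mL, about half of Cmax, so a BLQ value on that limb is unlikely. What survives is conditional: a log-down trapezoid cannot end at zero, and the SAP states no exception.

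**Conclusion.** The point holds for descriptive concentration summaries in cells where some but not all values are BLQ. There the written rule gives a geometric mean of exactly 0 and no geometric %CV, and nothing else in the SAP or protocol covers the case. No hypothesis test, sample size or safety conclusion depends on it.

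How many cells are affected cannot be settled from the documents. The half-life arithmetic points to Days 232 and 260; a reader might extend it to every washout visit, but about 56% and 31% of the level would remain at Days 190 and 204. The bias figures illustrate a lognormal with CV 80%. They run from +3.5% to +28% if zeros are dropped and should be read as that whole range.

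**What to change.** The rule is wrong as written and should be replaced in SAP 2.7.1:

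- Keep BLQ = 0 for the arithmetic mean, SD, %CV, median, minimum and maximum.
- For the geometric mean and geometric %CV, replace BLQ with a prespecified positive value, for example LLOQ/2.
- Report n (%) BLQ in every cell.
- Print not calculated for the geometric statistics when more than half of the cell's values are BLQ.
- As a conditional note in SAP 2.7.2: if a BLQ value falls on the declining limb, the linear rule applies to that segment of the AUC.

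The cost is SAP wording and a small programming change, with no new data. The substitute value and the one-half cutoff are conventions; what matters is fixing them in advance. The downside is that the geometric statistics then depend on the substitute. The dependence is mild for the geometric mean in large cells: in the n = 51 example it is 18.9 with LLOQ = 1 and 19.5 with LLOQ = 5. It is stronger for the geometric %CV (80% against 61%) and in small cells: at n = 9 the geometric mean is 13.1 against 15.7, and the geometric %CV 211% against 97%. That is a further reason to show the BLQ count beside them.
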